8.1.2.7 Reporting of Serious Adverse Events

Adverse events classified as serious require expeditious handling and reporting to Sponsor's monitoring CRO to comply with regulatory requirements. In general, reporting of Serious Adverse Events (SAEs) will begin at the time of first dosing on Cycle Day 1; however, SAEs occurring prior to first dosing may be reported if directly attributable to a study procedure.

For any serious adverse event (SAE) that occurs while a patient is on-study; within 30 days of the last study drug administration, regardless of any opinion as to the relationship of the SAE to the study drug; or if any SAE that the Investigator feels is related to the study drug occurs later than 30 days after the last study drug administration, the Sponsor or its designee must be notified immediately (within 24 hours of becoming aware of the event).

8.1.2.8 Safety Data Review

8.1.2.8.1 Safety Review Committee

A Safety Review Committee (SRC) comprises of 3 members – one Investigator, a representative from Heat Biologics and the Medical Monitor will evaluate the data obtained at each dose level including a review of all adverse events (serious and non-serious adverse events) as they are reported by the study site. The SRC will recommend whether the dose should be escalated as per protocol, revised to a lower level or

intermediate level, halted altogether or more patients are required at the same dose level to evaluate safety. If a DLT is observed already with the first patient treated in Cohort 1, the SRC may suggest and approve dose de-escalation with at least 50% reduction of HS-130 and HS-110 (dose level -1), depending on the nature of the reaction.

Ad-hoc SRC meetings may be called for by both the SRC and Sponsor any time during the study if DLTs are observed and/or new safety data warrants immediate action to the conduct of the trial (including events defined by the Study Stopping Criteria in Section 5.5).

The conclusion of the SRC meeting will be documented in meeting minutes. The outcome of the SRC meeting will be communicated to all Investigators.

8.2 Efficacy Assessments

Patient's disease status will be monitored by clinical and radiological assessment (CT scans or MRI) as per RECIST 1.1¹ criteria (Section 8.2.1). Patient response per RECIST 1.1¹ will be evaluated as complete response, partial response, stable disease, or progressive disease.

For the purpose of this study, patients will be evaluated after every 8-weeks \pm 1-week from C1D1. In the event objective response (PR or CR) is noted, changes in tumor measurements must be confirmed by repeat assessments that should be performed at least 4 weeks after the criteria for response are first met. For stable disease (SD), follow-up measurements must meet the SD criteria at least 6 weeks after study entry.

Response to immune therapies may occur after conventional determination of disease progression based on RECIST 1.1¹; therefore, at the Investigator's discretion patients may continue to receive the HS-130/HS-110 combination treatment after progressive disease is first observed.

8.2.1 RECIST 1.1 Criteria

8.2.1.1 Definitions

Response and progression will be evaluated in this study using the international criteria (version 1.1) proposed by the Response Evaluation Criteria in Solid Tumors (RECIST) Committee¹. Changes in only the largest diameter (unidimensional measurement) of the tumor lesions are used in the RECIST 1.1¹ criteria. Note: Lesions are either measurable or non-measurable using the criteria provided below. The term "evaluable" in reference to measurability will not be used because it does not provide additional meaning or accuracy.

8.2.1.2 Measurable Disease

Measurable disease is defined by the presence of at least one measurable lesion. Measurable lesions are defined as those that can be accurately measured in at least one dimension [longest diameter (LD) in the plane of measurement to be recorded] with a minimum size of:

- 10 mm by CT scan (CT scan slice thickness no greater than 5 mm)
- 10 mm caliper measurement by clinical exam (lesions which cannot be accurately measured with calipers should be recorded as non-measurable)
- 20 mm by chest x-ray

Malignant lymph nodes: To be considered pathologically enlarged and measurable, a lymph node must be ≥ 15 mm in short axis when assessed by CT scan (CT scan slice thickness no greater than 5 mm).

8.2.1.3 Non-measurable Disease

All other lesions (or sites of disease), including small lesions (longest diameter < 10 mm or pathological lymph nodes with ≥ 10 to < 15 mm short axis) are considered non-measurable disease. Lesions considered truly non-measurable include: leptomeningeal disease, ascites, pleural/pericardial effusions, lymphangitis cutis/pulmonis, inflammatory breast disease, abdominal masses/abdominal organomegaly identified by physical exam and not followed by CT or MRI.

Bone lesions, cystic lesions and lesions previously treated with local therapy must be considered as follows:

Bone lesions:

- Bone scan, PET scan or plain films are not considered adequate imaging techniques to measure bone lesions. However, these techniques can be used to confirm the presence or disappearance of bone lesions.
- Lytic bone lesions or mixed lytic-blastic lesions, with identifiable soft tissue components, that can be evaluated by cross sectional imaging techniques (i.e., CT or MRI) can be considered as measurable lesions if the soft tissue component meets the definition of measurability described above.
- Blastic bone lesions are non-measurable.

Cystic lesions:

- Lesions that meet the criteria for radiographically defined simple cysts should not be considered malignant lesions (neither measurable nor non-measurable) since they are, by definition, simple cysts.
- 'Cystic lesions' thought to represent cystic metastases can be considered measurable lesions, if they meet the definition of measurability described above. However, if non-cystic lesions are present in the same patient, these are preferred for selection as target lesions.

Lesions with prior local treatment:

- Tumor lesions situated in a previously irradiated area, or in an area subjected to other loco-regional therapy, are usually not considered measurable unless there has been demonstrated progression in the lesion.

8.2.1.4 Target Lesions

All measurable lesions up to a maximum of two lesions per organ and five lesions in total, representative of all involved organs, should be identified as target lesions and recorded and measured at baseline. Target lesions should be selected on the basis of their size (lesions with the longest diameter) and their suitability for accurate repeated measurements (either by imaging techniques or clinically). A sum of the diameters (longest for non-nodal lesions, short axis for nodal lesions) for all target lesions will be calculated and reported as the baseline sum diameters. The baseline sum diameters will be used as reference by which to characterize the objective tumor response.

8.2.1.5 Lymph Node Assessment

For lymph nodes, measurements should be made of the short axis, which is defined as perpendicular to the LD of node assessed in the plane of measurement:

- Target lesion if short axis ≥ 15 mm
- Non-target lesion if short axis is ≥ 10 but < 15 mm
- Normal if short axis < 10 mm

For baseline, add the actual short axis measurement to the sum of LD of non-nodal lesions.

8.2.1.6 Non-target Lesions

All other lesions (or sites of disease) including pathological lymph nodes should be identified as non-target lesions and should also be recorded at baseline. Measurements of these lesions are not required and these lesions should be followed as “present,” “absent,” or in rare cases “unequivocal progression.” In addition, it is possible to record multiple non-target lesions involving the same organ as a single item on the case report form (e.g., ‘multiple enlarged pelvic lymph nodes’ or ‘multiple liver metastases’).

8.2.1.7 Guidelines for Evaluation of Measurable Disease

All measurements should be taken and recorded in metric notation using a ruler or calipers. All baseline evaluations should be performed as closely as possible to the beginning of treatment and never more than 4 weeks before the beginning of the treatment.

Target lesions located in a previously irradiated areas should if possible be avoided, but such lesions may be designated as target lesions if clearly progressing (by RECIST 1.1¹ definition) at the latest evaluation prior to screening.

The same method of assessment and the same technique should be used to characterize each identified and reported lesion at baseline and during follow-up. Imaging-based evaluation is preferred to evaluation by clinical examination when both methods have been used to assess the antitumor effect of a treatment.

Clinical lesions. Clinical lesions will only be considered measurable when they are superficial and ≥ 10 mm diameter as assessed using calipers (e.g., skin nodules). In the case of skin lesions, documentation by color photography, including a ruler to estimate the size of the lesion, is recommended. When lesions can be evaluated by both clinical exam and imaging, imaging evaluation should be undertaken since it is more objective and may be reviewed at the end of the study.

Chest x-ray. Chest CT is preferred over chest x-ray, particularly when progression is an important endpoint. Lesions on chest x-ray may be considered measurable if they are clearly defined and surrounded by aerated lung.

Conventional CT and MRI. This guideline has defined measurability of lesions on CT scan based on the assumption that CT slice thickness is 5 mm or less. When CT scans have slice thickness > 5 mm, the minimum size for a measurable lesion should be twice the slice thickness. MRI is acceptable in certain situations (e.g., for body scans).

Ultrasound (US). US should not be used to measure tumor lesions. US examinations cannot be reproduced in their entirety for independent review at a later date because they are operator dependent. If new

lesions are identified by US, confirmation by CT or MRI is advised. If there is concern about radiation exposure at CT, MRI may be used instead of CT.

8.2.1.8 Response Criteria

8.2.1.8.1 Evaluation of Target Lesions

Complete Response (CR):	Disappearance of all target lesions. Any pathological lymph nodes (whether target or non-target) must have reduction in short axis to < 10 mm.
Partial Response (PR):	At least a 30% decrease in the sum of diameters of target lesions, taking as reference the baseline sum diameters.
Progressive Disease (PD):	At least a 20% increase in the sum of diameters of target lesions, taking as reference the smallest sum on study (this includes the baseline sum if that is the smallest). In addition to the relative increase of 20%, the sum must also demonstrate an absolute increase of at least 5 mm. The appearance of one or more new lesions is also considered progression.
Stable Disease (SD):	Neither sufficient shrinkage to qualify for PR nor sufficient increase to qualify for PD, taking as reference the smallest sum diameters while on study.

8.2.1.8.2 Assessment of Target Lymph Nodes

Lymph nodes identified as target lesions should always have the actual short axis measurement recorded (measured in the same anatomical plane as the baseline exam), even if the nodes regress to below 10 mm on study. In order to qualify for CR, each node must achieve a short axis < 10 mm. For PR, SD and PD, the actual short axis measurement of the nodes is to be included in the sum of target lesions.

8.2.1.8.3 Target Lesions that Become “too small to measure”

All lesions (nodal and non-nodal) recorded at baseline should have their actual measurements recorded at each subsequent evaluation, even when very small (e.g., 2 mm). If it is the opinion of the radiologist that the lesion has disappeared, the measurement should be recorded as 0 mm. If the lesion is believed to be present and is faintly seen but too small to measure, a default value of 5 mm should be assigned.

8.2.1.8.4 Lesions that Split or Coalesce on Treatment

When non-nodal lesions fragment, the longest diameters of the fragmented portions should be added together to calculate the target lesion sum. Similarly, as lesions coalesce, a plane between them may be maintained that would aid in obtaining diameter measurements of each individual lesion. If the lesions have truly coalesced such that they are no longer separable, the vector of the longest diameter should be the maximal longest diameter for the ‘coalesced lesion.’

8.2.1.8.5 Evaluation of Non-target Lesions

Complete Response (CR):	Disappearance of all non-target lesions and normalization of tumor marker level. All lymph nodes must be non-pathological in size (< 10 mm short axis).
Non-CR/Non-PD:	Persistence of one or more non-target lesion(s) and/or maintenance of tumor marker level above the normal limits.
Progressive Disease (PD):	Unequivocal progression of existing non-target lesions. (The appearance of one or more new lesions is also considered progression.) To achieve ‘unequivocal progression’ on the basis of the non-target disease, there must be an overall level of substantial worsening in non-target disease such that, even in the presence of SD or PR in target disease, the overall tumor burden has increased sufficiently to merit discontinuation.

8.2.1.8.6 New Lesions

The finding of a new lesion should be unequivocal (i.e., not attributed to differences in scanning technique, change in imaging modality, or findings thought to represent something other than tumor, such as a ‘new’ healing bone lesion). A lesion identified on a follow-up study in an anatomical location that was not scanned at baseline is considered a new lesion and will indicate disease progression. If a new lesion is equivocal, continued therapy and follow-up evaluation will clarify if it represents truly new disease. If repeat scans confirm this is definitely a new lesion, then progression should be declared using the date of the initial scan.

8.2.1.9 Evaluation of Best Overall Response

The best overall response is the best response recorded from the start of the treatment until disease progression/recurrence (taking as reference for progressive disease the smallest measurements recorded since the treatment started). The patient’s best overall response assignment will depend on findings of both target and non-target disease and will also take into consideration the appearance of new lesions. Furthermore, depending on the nature of the study, it may also require confirmatory measurement. Specifically, in non-randomized trials where response is the primary endpoint, confirmation of PR or CR is needed to deem either one the “best overall response.”

It is assumed that at each protocol-specified time point, a response assessment occurs ([Table 4](#)) provides a summary of the overall response status calculation at each time point for patients who have measurable disease at baseline. When patients have non-measurable disease, ([Table 5](#)) should be used.

Table 4: Time point response: Patients with target (+/- non-target) disease

Target Lesions	Non-target Lesions	New Lesions	Overall Response
CR	CR	No	CR
CR	Non-CR / non-PD	No	PR
CR	Not evaluated	No	PR
PR	Non-PD or not all evaluated	No	PR
SD	Non-PD or not all evaluated	No	SD
Not all evaluated	Non-PD	No	NE

PD	Any	Yes or No	PD
Any	PD	Yes or No	PD
Any	Any	Yes	PD
CR=complete response, PR=partial response, SD=stable disease PD=progressive disease, NE=inevaluable			

Table 5: Time point response: Patients with non-target disease only

Non-target Lesions	New Lesions	Overall Response
CR	No	CR
Non-CR / non-PD	No	Non-CR / non-PD*
Not all evaluated	No	NE
Unequivocal PD	Yes or No	PD
Any	Yes	PD
CR=complete response; PD=progressive disease; NE=inevaluable * Non-CR/non-PD is preferred over SD for non-target disease		

Best response determination for studies where confirmation of CR or PR is required:

Complete or partial responses may be claimed only if the criteria for each are confirmed by a repeat assessment at least 4-weeks later. In this circumstance, the best overall response can be interpreted as in (Table 6).

Table 6: Best overall response when confirmation of CR and PR required

Overall response First time point	Overall response Subsequent time point	BEST overall response
CR	CR	CR
CR	PR	SD, PD or PR*
CR	SD	SD provided minimum criteria for SD duration met, otherwise PD
CR	PD	SD provided minimum criteria for SD duration met, otherwise PD
CR	NE	SD provided minimum criteria for SD duration met, otherwise NE
PR	CR	PR
PR	PR	PR
PR	SD	SD
PR	PD	SD provided minimum criteria for SD duration met, otherwise PD
PR	NE	SD provided minimum criteria for SD duration met, otherwise NE
NE	NE	NE
CR=complete response; PR=partial response; SD=stable disease; PD=progressive disease; NE=inevaluable * If CR is truly met at first time point, then any disease seen at a subsequent time point, even disease meeting PR criteria relative to baseline, makes the disease PD at that point (since disease must have reappeared after CR). Best response would depend on whether minimum duration for SD was met. However, sometimes 'CR' may be claimed when subsequent scans suggest small lesions were likely still present and in the fact patient had PR, not CR, at the first time point. Under these circumstances, the original CR should be changed to PR and the best response is PR.		

8.2.1.10 Confirmatory Measurement/Duration of Response

8.2.1.10.1 Confirmation

To be assigned a status of PR or CR, changes in tumor measurements must be confirmed by repeat assessments that should be performed at least 4 weeks after the criteria for response are first met. In the case of SD, follow-up measurements must have met the SD criteria at least once after study entry at a minimum interval of 6-weeks.

8.2.1.10.2 Duration of Overall Response

The duration of overall response is measured from the time measurement criteria are met for CR or PR (whichever is first recorded) until the first date that recurrent or progressive disease is objectively documented (taking as reference for progressive disease the smallest measurements recorded since the treatment started).

The duration of overall CR is measured from the time measurement criteria are first met for CR until the first date that recurrent disease is objectively documented.

8.2.1.10.3 Duration of Stable Disease

Stable disease is measured from the start of the treatment until the criteria for progression are met, taking as reference the smallest measurements recorded since the treatment started.

8.3 Best Overall Response

The best overall response is the best response (CR, PR, SD) recorded from the start of the study treatment until disease progression/recurrence, taking into account any requirement for confirmation.

8.4 Overall Survival (OS)

OS will be calculated as the duration of survival from the date of first HS-130/HS-110 combination treatment until the date of death from any cause. If the date of death is not available, OS will be censored at the date the patient was last known to be alive.

8.5 Progression-free Survival (PFS)

Progression-free survival (PFS) is defined for each patient as the time from date of first HS-130/HS-110 combination treatment to the date of the first documented tumor progression (per RECIST 1.1¹) or death due to any cause. Patients who die without a reported prior progression will be considered to have progressed on the date of their death. Patients who did not progress or die will be censored on the date of their last evaluable tumor assessment. Patients who started any subsequent anticancer therapy without a prior reported progression will be censored at the last evaluable tumor assessment prior to the initiation of the subsequent anticancer therapy.

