7.0 STUDY EVALUATIONS

7.1 Schedule of Study Evaluations

Study evaluations are summarized in [Table 3](#) and described in Sections [1.1](#) through [7.6](#).

Table 3: Schedule of Assessments

	Pre-treatment	Cycle 1 (± 2 days) ^p		Cycle 2 (± 2 days) ^p		Cycle 3 and beyond (± 2 days) ^p	30-day safety follow up visit (±3 days) ^m	Post-treatment Follow-up (±1 week) ⁿ	Survival Follow-up (±2 week) ^o	
		Day 1	Day 8	Day 1	Day 8	Day 1				
Informed consent	X ^a									
Medical history	X ^a									
Physical exam	X ^b	X ^b	X	X	X	X	X			
Weight	X ^b	X ^b	X	X	X	X	X			
Vital signs ^c	X ^b	X	X	X	X	X	X			
ECG ^d	X ^a	X		X		X	X			
ECOG performance status	X ^b	X ^b	X	X	X	X	X			
Tumor measurement ^e	X ^a					X ^e		X ⁿ		
Hematology ^f	X ^b	X ^b		X		X	X			
Blood chemistry ^g	X ^b	X ^b		X		X	X			
Pregnancy test ^h	X ^b									
Blood Sample for Immune Response Labs ⁱ		X ⁱ	X ⁱ	X ⁱ	X ⁱ		X			
Blood sample for cytokines/chemokines ^j		X ⁱ		X ⁱ		X ⁱ				
Biopsy ^k	X ^a					X ^k				
HS-130 and HS-110 administration ^l		X		X		X				
Concomitant medications/Treatment	X ^a	←..... Throughout Study→						X	X	X ^o
Adverse events		←..... Throughout Study→						X	X	
Survival Status									X ^o	

- a: Within 28 days prior to treatment.
- b: Within 7 days prior to treatment. For Cycle 1 Day 1, these tests may be performed within 3 days. Tests done within 3 days of Cycle 1 Day 1 do not need to be repeated unless clinically indicated.
- c: Vital signs, including blood pressure, heart rate, respiratory rate, and temperature. During Cycle 1 and Cycle 2 on Day 1: Before HS130/HS110 treatment; after treatment at 30 mins (± 5 min), 1hr (± 5 min). Other Cycles on Day 1: only Pre-dose.
- d: Standard 12-lead ECG (in triplicate) while patient is in semi-recumbent position pre-dose on Day 1 of each cycle.
- e: Tumor measurement per RECIST 1.1¹. Patients will be evaluated at screening and then after every 8-weeks ± 1 week from C1D1 until disease progression.
- f: Hematology, including hemoglobin, WBC with differential, and platelet count (Approximately 5 mL blood per draw).
- g: Blood chemistry, including sodium, potassium, BUN, glucose, SGOT/SGPT (ALT/AST), alkaline phosphatase, total protein, total bilirubin, albumin, lactate dehydrogenase (LDH), TSH, creatinine, C-reactive protein and calcium. (Approximately 5 mL blood per draw).
- h: Pregnancy test; for women of childbearing potential, a negative pregnancy test (urine or serum) must be documented.

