9.1 Analysis Populations

Safety Evaluable Population: All patients who received at least 1 dose of the study treatment.

Efficacy Evaluable Population: All patients with pre-treatment measurable disease by RECIST 1.1¹, who had at least one radiological assessment after pre-treatment or discontinued study treatment early due to disease progression.

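### Section 8.5 does not limit PFS censoring to post-baseline assessments, so a patient with no on-study scan can get a PFS time of -28 to 0 days

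*Combined protocol and SAP*

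**What the plan says.** Section 8.5 defines PFS as "the time from date of first HS-130/HS-110 combination treatment to the date of the first documented tumor progression" or to death. Three further sentences fix the dates:

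- No progression and no death: "Patients who did not progress or die will be censored on the date of their last evaluable tumor assessment".
- New anticancer therapy without a reported progression: the patient "will be censored at the last evaluable tumor assessment prior to the initiation of the subsequent anticancer therapy".
- Death: "Patients who die without a reported prior progression will be considered to have progressed on the date of their death".

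On scan timing, note e to Table 3 (section 7.1) says: "Patients will be evaluated at screening and then after every 8-weeks ± 1 week from C1D1 until disease progression". Note a to that table places the screening measurement "Within 28 days prior to treatment", and section 8.2.1.7 requires baseline evaluations "never more than 4 weeks before the beginning of the treatment".

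On who is analysed, section 9.4 has PFS determined for every patient and names no analysis population. The Efficacy Evaluable Population in section 9.1 requires a radiological assessment after baseline, but also admits patients with measurable disease who had none "or discontinued study treatment early due to disease progression". Section 9.0 lists n, mean, median, standard deviation and range, as appropriate, by dose cohort. It names no Kaplan-Meier method.

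**The concern.** The time origin is the first dose, but the censoring date is tied to an assessment that may precede it. For a patient never scanned on study, the only tumor assessment on record is the screening one. Taken at its word, section 8.5 then dates the end of follow-up before its start, and PFS is negative.

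Such a patient is foreseeable. Withdrawal, loss to follow-up, adverse events and investigator decision are all listed reasons for stopping (section 5.4), and section 5.4.2 provides for replacing patients who leave during Cycles 1 and 2. No imaging is planned at the 30-day safety visit (section 7.4). Imaging after treatment is every 12 weeks from the last dose and ends when a new treatment starts (section 7.5).

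At stake is a clean derivation of a secondary endpoint. Without a stated rule, whoever programs PFS must decide after seeing the data whether to keep the negative value, set it to zero or leave the patient out.

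**Working it through.** The plan gives no figure that depends on this rule, so there is nothing to reproduce. The check is date arithmetic.

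**Inputs**
- Origin: date of first combination dose, C1D1 (section 8.5).
- Screening scan: 0 to 28 days before treatment (Table 3 note a; section 8.2.1.7).
- First on-study scan: week 8 ± 1 from C1D1, that is 7 × 7 = 49 to 9 × 7 = 63 days (Table 3 note e).
- Patients: 13 to 30 in all (section 9.6). Table 2 sets a minimum of 3 in each of cohorts 2 to 4, and of 1 at each dose level within cohort 1.

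**Step 1: the derived time.** PFS time = censoring date - date of first dose. With the screening scan as the last assessment:

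| Screening scan, days before first dose | PFS time (days) | With a +1 day convention |
|---|---|---|
| 28 | -28 | -27 |
| 14 | -14 | -13 |
| 7 | -7 | -6 |
| 1 | -1 | 0 |
| 0 | 0 | +1 |

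Section 8.5 does not say whether one day is added. Without it, the result is negative unless the scan was on the dosing day.

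**Step 2: who is affected.** Two groups have no on-study assessment to censor at:
- patients with no post-baseline assessment, no documented RECIST progression and no death;
- patients who start new anticancer therapy before any on-study scan, because the second censoring sentence also looks back to the last assessment.

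A no-scan patient who dies without having started new therapy is an event at the date of death, with a positive time. If new therapy came first and death later, the subsequent-therapy sentence points to the screening scan and the death sentence points to the date of death. Section 8.5 does not say which prevails.

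**Step 3: effect on the summaries.** Assume the largest gap. Replacing 0 by -28 in one patient lowers the mean of n values by 28/n days:
- n = 3: 28/3 = 9.3 days
- n = 13: 28/13 = 2.2 days
- n = 30: 28/30 = 0.9 days

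At a dose level with one patient, the value would be the mean, the median and both ends of the range.

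For illustration, take 13 invented patients: six at 56 days, four at 112, two at 168, and one with no on-study scan. The first twelve sum to 336 + 448 + 336 = 1,120.
- No-scan patient at 0: mean 1,120/13 = 86.2, minimum 0.
- No-scan patient at -28: mean 1,092/13 = 84.0, minimum -28.
- The raw median is 56 in both cases.

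**Step 4: effect on Kaplan-Meier.** A patient censored at or before time 0 is in no risk set at any later event time. In the illustration 12 patients are at risk at 56 days either way. With 6, 3 and 1 events at the three times, the survival estimates are 0.5, 0.25 and 0.125 in both cases.

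**The case against.** **A post-baseline reading is plausible.** Section 8.2.1.1 says that evaluable will not be used to describe measurability. Table 4 uses evaluability for a time-point response, which a screening scan cannot have. A sensible programmer might therefore read the phrase as post-baseline. This stands as a reason to expect the right intent. It does not settle the matter, because Table 3 note e speaks of patients being evaluated at screening, and even the post-baseline reading leaves no-scan patients with no censoring date.

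**The group is narrow.** Progression can be documented before week 8, since section 8.2 allows clinical as well as radiological assessment and new lesions count. Patients who stop for other reasons are still imaged every 12 weeks. This stands.

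**Stronger readings that the documents do not support.**
- A reader might infer that section 9.1 places the affected patients in the analysis. It does so only for those who stopped early for a progression that was not documented per RECIST 1.1. A documented progression is an event with a positive time. Patients who withdraw or are lost before any scan fall outside that population. Equally, no section ties PFS to it, so it does not close the gap.
- A reader might rest the point on section 9.4 deriving PFS for each patient. That is weak evidence of an analysis set, because the same sentence covers best overall response.
- A reader might infer that treated patients are lost from the PFS risk set and the curve is biased. Censoring at Day 1 adds no follow-up either, and Step 4 shows the estimates unchanged. How software treats negative times is not in the documents.
- A reader might want a percentage of patients affected. The documents give no dropout rate, so any such figure would be an assumption.

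**Conclusion.** The point holds as a minor defect in a derivation rule. On its literal wording, section 8.5 gives a PFS time of -28 to 0 days for a treated patient without a post-baseline assessment, documented progression or death, and for one who starts new anticancer therapy before any on-study scan.

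The consequence is limited. PFS is one of several descriptive secondary endpoints. Dose escalation and the MTD rest on DLTs and safety data, and PFS is not named among the grounds for choosing the RP2D (sections 6.1.1 and 6.1.3). A Kaplan-Meier estimate would be unaffected. What could be distorted is the reported n (if the value is set aside), the mean and with it the standard deviation, the minimum, or the listed value in a small cohort.

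The sizes in the working assume the largest gap of 28 days, one affected patient and, in the 13-patient example, invented times for the rest. They also assume that a mean of PFS times is reported at all. Section 9.0 lists means only as appropriate and does not mention PFS.

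**What to change.** Three changes to section 8.5:

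1. In both censoring sentences, define the last evaluable tumor assessment as one made after baseline.
2. Add that a patient with no evaluable post-baseline assessment, and with neither documented progression nor death before any new anticancer therapy, is censored at the date of first dose (Day 1).
3. State whether a death after the start of new anticancer therapy is a PFS event or is censored under the subsequent-therapy sentence. If it is to be an event, write that exception into the Day 1 sentence, so that a no-scan patient who starts new therapy and later dies has exactly one date.

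The cost is a few words in two sentences and two added sentences. No visit, scan, treatment or data item changes. The choice should be made before PFS is derived.
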